#### I. Potential Limitations & Proposed Solutions

Limitations of the study relate to the potential loss to follow-up. From our preliminary data, we have determined that even the addition of a single specially trained student improved successful telephone contacts substantially. Therefore, within the context of a specifically dedicated study staff and the other enhancements, it is anticipated that further improvement in successful telephone contacts can be achieved. Furthermore, a large percentage of individuals in the pilot studies are followed in the OSU health system, simplifying the access to follow-up data at 24 weeks. Finally, there may be some difficulty discerning whether the discharge instruction or the nursing support were the primary determinants of success. We already know that education alone is of limited value for in the management of chronic illness. The purpose of the study is really to serve as a model of a comprehensive discharge program with the intent to maximize potential benefits of its individual elements.

#### J. Work Plan and Timeline

The overall project is anticipated to last 3 years (Table 10). The first 3 months will involve project start-up activities, including development of the REDCap database, regulatory submission, and training study staff. Study recruitment and enrollment will commence during the second quarter of the first study year and is anticipated to last 18 months to achieve a final enrolled sample of 222 participants. The final visit is expected at 6 months post-enrollment. Data gathering activities are scheduled to take 3 additional months. Data processing activities will commence at the start of data gathering and continue through the 33 months. The last quarter of Study Year 3 will be spent preparing reports and manuscripts. It is anticipated that at least 2 posters and 2 manuscripts will be generated from this work, including the first manuscript demonstrating improved processes of care at discharge and the second manuscript demonstrating change in glycemic control, titration and persistence of insulin.

Table 10. Study Timeline

Activities	Year 1				Year 2				Year 3			
	Q1	Q2	Q3	Q4	Q1	Q2	Q3	Q4	Q1	Q2	Q3	Q4
Start-up procedures	X											
Recruit & enroll sample		X	X	X	X	X	X					
Follow-up visits			X	X	X	X	X	X				
Data analysis									X	X		
Prepare reports & manuscripts										X	X	

## **Summary and Future Directions**

For the hospitalized patient, multiple factors collude to impede successful transitions in care in the current fragmented health system. Diabetes provides a suitable framework for chronic disease management in general due to its complexity regarding therapies, self-care, and multiple comorbidities. This proposal seeks to redefine the role of diabetes management throughout the continuum of care. Future applications would include multi-center studies and studies to determine the efficacy of the individual components.

Appendix: Diabetes Discharge Orderset		➤ Drop-down Choices
Diet — Note: Most patients will require consistent carbohydrate diet		
➤ Consistent carbohydrate diet Note: appropriate for most patients, including those discharging to skilled nursing		 45 grams per meal  60 grams per meal
 Flexible carbohydrate diet Note: carbohydrate counting method, only if patient using prior to hospitalization or has demonstrated competency		
Follow-up		
➤ Primary Care Provider	[see below]	
➤ Endocrinologist Note: If patient does not live near Columbus, please locate an Endocrinologist nearest to their home. The phone number for OSU Endocrinology is [contact]	 Call for an appointment. You should be seen within 2 weeks of discharge from the hospital, your diabetes medications may need adjustment  Call for an appointment. You should be seen within *** weeks  You have a follow-up appointment with *** on [date]	
➤ Diabetes Education Note: If patient does not live near Columbus, please locate a diabetes educator nearest to their home. The phone number for OSU Endocrinology is [contact]	 Survival skills  General diabetes education	
 Bring a blood sugar log (record of your glucose readings), medications and glucose meter with you.		
Notify Physician		
 Call your healthcare provider if you are having recurrent low sugars (less than 70 mg/dl) more than 2 days in a row or if you have any severe low sugars requiring the assistance of someone else to treat.		
 Call your healthcare provider if you have recurrent high (above 250 mg/dl) blood sugars for more than 3 days in a row, or if you have glucose readings over 250 mg/dl with new symptoms such as nausea, vomiting, or dizziness.		
Patient Instructions		
 Your target glucose is *** mg/dl fasting and under *** mg/dl nonfasting  <Note: Typical blood sugar goals for many people are 80-130 mg/dl in the mornings (fasting) and less than 180 mg/dl throughout the rest of the day>		
 Instructions for Managing Your Diabetes at Home	[Attachment]	
Diabetes Medication and Supply: Note: U100 Insulin vials contain 1000 units, U100 pens contain 300 unit/pen, glargine U300 contains 450 unit/pen, degludec U200 contains 600 unit/pen, lispro U200 contains 600 unit/pen. [each prescription option is paired with U100 0.3 or 0.5 ML syringe or pen needles as appropriate]		
➤ Basal Insulin	 [Example Drop-down Menu:]  Insulin Glargine 300 unit/ml pen *** units every day.  Increase *** unit every 4 days until AM (fasting) glucose is under *** mg/dl, provided that you have no glucoses under 80 mg/dl, do not go above *** unit per day.	
➤ Glargine U100 Solostar pen and pen needles ➤ Glargine U300 Solostar pen and pen needles ➤ Detemir U100 FlexTouch pen and pen needles ➤ Degludec U100 FlexTouch pen and pen needles ➤ Degludec U200 FlexTouch pen and pen needles ➤ Glargine U100 vial and syringes		

 
➤ Detemir U100 vial and syringes
 
➤ NPH U100 vial and syringes
 
	 [Cardiac surgery patients]: Reduce dose by 2 unit every day that you wake up with a glucose less than 100 mg/dl or if you have any glucose levels under 80 mg/dl.  No titration Dispense: 3 prefilled pens; Refills: 1  Pen needle 31 G x 4 mm For use with insulin once daily Dispense: 50; Refills: 1														

➤ Set Meal Insulin Dose: appropriate for most patients using prandial insulin in addition to consistent carbohydrate diet
 
 
➤ Aspart U100 Flextouch pen and pen needles
 
➤ Glulisine U100 Solostar pen and pen needles
 
➤ Lispro U100 Kwikpen and pen needles
 
➤ Lispro U200 Kwikpen and pen needles
 
➤ Aspart U100 vial and syringes
 
➤ Lispro U100 vial and syringes
 
	
[Example Drop-down Menu:]
 
➤ Insulin Glulisine 100 Unit/ML Pen-injector      *** units SQ QAC.
 
 High dose correction
 
➤ Standard correction
 
 
 If your glucose is this	Add this much insulin to your mealtime dose	
 
 150-199	1	
 
 200-249	2	
 
 250-299	3	
 
 300-349	4	
 
 350-400	5	
 
 Over 400	6	
 
 
 Low dose correction
 
Dispense: 3 prefilled pens; Refills: 1
 
 Pen needle 31 G x 4 mm
 
For use with insulin 4 times daily
 
Dispense: 150; Refills: 1
	If your glucose is this	Add this much insulin to your mealtime dose	150-199	1	200-249	2	250-299	3	300-349	4	350-400	5	Over 400	6
If your glucose is this	Add this much insulin to your mealtime dose														
150-199	1														
200-249	2														
250-299	3														
300-349	4														
350-400	5														
Over 400	6														

➤ Flexible Meal Insulin Dose: appropriate ONLY if patient using prior to hospitalization, discharging to Dodd Hall or demonstrates competency, in addition to flexible carb diet
 
 
➤ Aspart U100 Flextouch pen and pen needles
 
➤ Glulisine U100 Solostar pen and pen needles
 
➤ Lispro U100 Kwikpen and pen needles
 
➤ Lispro U200 Kwikpen and pen needles
 
➤ Aspart U100 vial and syringes
 
➤ Lispro U100 vial and syringes
 
	
[Example Drop-down Menu:]
 
➤ Insulin Glulisine 100 Unit/ML Pen-injector      1 unit for every *** grams of carbohydrate SQ QAC.
 
 High dose correction
 
➤ Standard correction
 
 
 If your glucose is this	Add this much insulin to your mealtime dose	
 
 150-199	1	
 
 200-249	2	
 
 250-299	3	
 
 300-349	4	
 
 350-400	5	
 
 Over 400	6	
 
 
 Low dose correction
 
Dispense: 3 prefilled pens; Refills: 1
 
 Pen needle 31 G x 4 mm
 
For use with insulin 4 times daily
 
Dispense: 150; Refills: 1
	If your glucose is this	Add this much insulin to your mealtime dose	150-199	1	200-249	2	250-299	3	300-349	4	350-400	5	Over 400	6
If your glucose is this	Add this much insulin to your mealtime dose														
150-199	1														
200-249	2														
250-299	3														
300-349	4														
350-400	5														
Over 400	6														

Glucose Monitoring
 
 
➤ Once per day (non-insulin requiring patients)
 
➤ 4 times per day before meals and at bedtime
 
➤ 6 times per day (before and 2 hours after meals)
 
	
[Example Drop-down Menu:]
 
 Glucose monitor (if patient does not have one at home)
 
Dispense: 1; Refills: 0
														

	 Glucose test strips Testing 4 times per day, ICD-10: *** Dispense 150; Refills: 1  Lancets Testing 4 times per day, ICD-10: *** Dispense 150; Refills: 1  Alcohol wipes Testing 4 times per day, ICD-10: *** Dispense 150; Refills: 1
 Ketostix strips (for Type 1 DM or history of DKA) Test urine prn glucose >400 mg/dl or >250 mg/dl with nausea, vomiting or other symptoms of DKA Dispense 50; Refills: 0	
 Glucagon emergency kit (for Type 1 DM or history of severe hypoglycemia or hypoglycemia unawareness) 1 mg SQ prn severe hypoglycemia Dispense 1; Refills: 0	

## HUMAN SUBJECTS

### A. Protection of Human Subjects

#### A.1 Risk to human subjects

##### A.1.a *Human Subjects involvement, characteristics, and design*

This is a randomized controlled trial of the use of a discharge order set (DOS) with post-discharge nursing support in hospitalized patients with poorly controlled diabetes. The outcomes include glycemic control (HbA1c), persistence of insulin use and adequate dose titration, and discharge processes of care, measured in terms of clarity of instructions, adequacy and completeness of prescriptions for insulin and diabetes supplies, and follow-up plan. Patients in the standard group will receive basal insulin and otherwise enhanced standard care. Patients in the intervention group will undergo utilize a diabetes focused discharge order set and instructions for specific dose titration with nurse follow-up contacts at 2 and 6 weeks following discharge. Records will be obtained from primary physicians if needed. Specific medical concerns will be forwarded to the primary provider, who will receive a packet at discharge that will assist with transition of the patient's care to the community and updates at 3 months. HbA1c and diabetes empowerment, is checked at baseline and 12 and 24 weeks for both groups. Outcomes are assessed at 2, 6, 12 and 24 weeks.

The sample is obtained from two hospitals from a single academic medical center. The main campus hospital consists of University hospital, Ross Heart Hospital, James Cancer Hospital, and Brain and Spine hospitals and has a referral base from central and southern Ohio as well as a diverse array of medical and surgical patients. OSU East is a community hospital that serves a large percentage of local, often indigent patients. A total of 222 participants are planned, approximately 80% from the main hospital. Data will be entered into REDCap from both sites via an online secure database tool. Completed informed consent and questionnaires will be scanned into this system as well. The OSU electronic medical record has the capability of designating the patient is enrolled in a research study in order to improve communication between providers and patients.

Based upon preliminary data, we found that approximately 30% were of African American race. We are enrolling a wide age range, 25-75, in order to achieve optimal external validity, but have excluded the younger and older participants due to insufficient numbers in those ranges and possibly different educational needs, that may involve people (family) other than the patient. Participants are anticipated to be sick and have other comorbidities (in our pilot data, 70% were admitted for a problem that was not directly related to diabetes). However, all participants will be free-living in the community and have a phone. Due to bias introduced by additional support staff at institutions such as nursing homes and rehabilitation centers, these participants will be excluded. Participants who are unable to provide consent in English will be excluded as this number is very small and will hinder motivational interviewing (MI) process. Other vulnerable populations, such as prisoners will be excluded. Pregnant individuals will be excluded since the HbA1c is not as reliable and because such individuals have different motivations and follow-up already in place.

Permission will be obtained from the attending physician of the admitting inpatient service prior to approaching participants for enrollment. Randomization will be conducted using a computerized random number generator program that is weighted and will be stratified by race. The frequency of telephone follow-up is felt to be adequate to establish reasonable endpoints for reinforcement of behavior and capture a realistic window for readmission.

##### A.1.b. *Sources of Materials*

- Blood work will be collected for HbA1c at baseline and follow-up.

- Data that will be collected for both groups include:
  - Contact information, including email address and best times to reach the patient, contact information for two emergency contacts, and contact information of the patient's primary care provider
  - Type of diabetes, complications, duration
  - Education level, marital status, work status, home ownership, medical coverage, and demographics
  - Social support, measured using the Multidimensional Scale of Perceived Social Support.
  - Reason for hospital admission, medical history, concomitant medications, weight, height, BMI, standard of care lab results
  - Functional health literacy assessment.
  - Diabetes Empowerment Scale Short-Form (DES-SF): The DES-SF will be obtained at baseline and follow-up
  - Charlson comorbidity index
  - Blood Sugar Log
  - Outcomes including readmission or other acute care services, outpatient physician follow-up, medication adherence. Records will be requested from outpatient providers as needed.

#### *A.1.c. Potential Risks*

There are no physical risks that would not otherwise be anticipated, as the blood draw for HbA1c is considered standard of care. No specific prescriptive regimen for medications is planned and therefore this also represents standard of care. Furthermore, we already know that this is a high-risk population. Psychological harm may be a possibility if participants neglect other aspects of self-care in favor of diabetes. However, this seems unlikely and will be averted with frequent contact and anticipated increased outpatient follow-up. No financial or legal consequences are anticipated. Breach of confidentiality is a possibility but with standard procedures for immediate entry of paper data into the secure online database, use of a study identification code on all data gathering instruments, and the use of electronic health records, this should be limited.

Other forms of contact, such as internet, could be considered but this would not be a viable forum for all patients. Therefore, email (in secure mail format) will be reserved for follow-up of specific problems or in the event of failure to contact the patient.

### **A.2 Adequacy of Protection Against Risks**

#### *A.2.a Recruitment and Informed Consent*

Potential participants will be identified during their hospitalization through screening inpatient medicine and surgery wards. A partial HIPAA waiver will be obtained for this purpose. Permission will be obtained from the admitting team's attending physician or appropriate designee. The patient will be approached in private. Personnel (coordinator) will describe the purpose of the study in the same words that are used on the consent form, which states lack of participation will not otherwise influence patient care. Participants are expected to read the consent form (or have it read to them) in full and be able to explain the study purpose, risks, and procedures to the investigator before consent will be considered complete and informed. Participants will be encouraged to ask questions and have any questions answered to their satisfaction. Participants that seem unsure or want to consider it further will be re-approached with their permission, after several hours or the following day or otherwise per the participant's request. The samples and study-related information will not be used if the participant subsequently declines enrollment.

#### **A.2.b. Protections against risk**

Participants will be assigned a study number that will be the primary means of identifying patient data. A key will be kept on the secure endocrine network drive but this will only be for internal investigator use. Any personal information acquired will be entered into the secure online database (REDCap), which is password protected, and allows limited access to varying degrees. Only immediate study staff (PI, nurse, research assistants) will have access to REDCap. Other personal information (such as signed consent forms) will be kept in the office of the PI or the study coordinator and locked when not in use. Personal data that is otherwise not recorded into the database will be destroyed immediately through appropriate confidential shredding bins. After the program is complete and the data has been analyzed, identifiable/coded(linked) data will be retained and stored confidentially for the minimum required amount of time. Personally identifiable past medical history and study data (glucose, laboratory assessments) will be obtained from EPIC/IHIS, REDCap and the chart reviews. No highly sensitive information (mental illness, HIV status, social security number) will be collected and vulnerable populations such as prisoners will not be enrolled.

During phone call follow-ups, diabetes-specific events will be referred to the participant's primary provider with use of the study nurse or PI as back-up for urgent matters only. Study-related adverse events will be recorded and severe adverse events will be reported to the study PI and the institutional review board. Any severe adverse events felt to be related to the study will be reported immediately to the PI and IRB. Participants may leave the study for any reason and are assured that this will not otherwise affect their care. Thus, informed consent is treated as a continual process.

#### **A.3. Potential Benefits of the Proposed Research to Human Subjects and Others**

Participants may benefit from more intensive interaction with study staff, through improved glycemic control as well as close follow-up and anticipatory guidance. Benefits to society include improved glycemic control and hospital readmission, which may result in reduced medical costs, particularly among uninsured individuals. The risks are primarily related to breach of confidentiality and are limited, though still possible. Given the safeguards that are put in place, the potential benefits should outweigh the risks.

#### **A.4. Importance of the Knowledge to be Gained**

The importance of the knowledge is in the understanding of the role of diabetes, in particular diabetes education and PN, on the discharge process. Currently, diabetes is overlooked in the hospital and at discharge, despite its importance for the overall well-being of the patient. The current protocol provides an easily adaptable hierarchical process for inpatient to outpatient transitions in care for a population of complicated medical patients. Currently, few randomized studies have examined whether telephonic follow-up or post-discharge support is effective in this population. The rising epidemic of diabetes will continue to contribute significantly to the morbidity of these patients, frequently necessitating hospital care. Providing solutions to this problem is of considerable urgency. Therefore, the potential benefits outweigh the given the aforementioned risks.

#### **A.5. Data and Safety Monitoring Plan**

*The Data and Safety Monitoring Plan is written to ensure the safety of the participants and to verify the validity and integrity of the data.*

##### **1. Study risk assessment:**

**Exempt** (protocols exempt from IRB review are *not* required to submit a DSMP)

**Level I risk** (identify ***all*** applicable study procedures)

 Anthropometric evaluations	 DEXA scans
 Electrocardiograms (ECG)	 Exercise testing
 Intravenous glucose tolerance tests (IVGTT)	 Intravenous catheter insertion
 Computerized Axial Tomography (CAT) or Magnetic Resonance Imaging (MRI)	 Observational/Behavioral studies
 Oral glucose tolerance tests (OGTT)	 Pathology slide review
 Special or prescribed diets/Nutritional studies	 Venipuncture
 Other low risk non-therapeutic tests or studies (list):	

**Level II risk** (identify ***all*** applicable study procedures)

 Child population	 Normal volunteers using well-described research procedures
 Endoscopy	 Vulnerable population(s), e.g. minorities, indigent, MRDD, prisoners, military personnel, individuals with diminished capacity for decision-making and/or limited literacy skills (e.g. <8 th grade reading level)
 Elderly population	 Pharmaceutical agent(s) under study/Phase IV (post-marketing) studies
 Insulin clamp	 Pregnant population
 Muscle biopsy	 Psych. or neuro. impaired population
 Research-associated procedures (please specify):	
Other moderate risk non-therapeutic tests or studies (please specify):	

The risks for the actual study procedures are considered low as the intervention is limited to behavioral strategy with a blood draw that is otherwise considered to be standard of care. Study-related adverse events, enrollment compliance, proper informed consent, data analysis, confidentiality will be reviewed annually by the study PI and independent safety advocate ([name]).

## **2. Plan for reporting adverse events and unanticipated problems:**

Adverse event and unanticipated problem reporting will comply with University, as well as Federal guidelines, as appropriate. All adverse events and unanticipated problems will be reported to the IRB, and to the funding agency as well as other entities, as required. Such events or problems requiring reporting include those that may involve physical, psychological, social, legal and/or economic harms to the participants. Adverse events

will include severe hypoglycemia rates (defined as hypoglycemia associated with seizure or hemodynamic compromise in need of outside assistance), pregnancy, overdose, and breach of confidentiality. In addition the following definitions apply:

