#### **F.1.b. Follow-up Encounters**

Study staff will conduct phone calls or email communications at 2 and 6 weeks to confirm contact information and inquire about discharge follow-up. Patients will be given an appointment day and time prior to discharge for the first phone contact at 2 weeks. Any specific medical concerns reported during any call will be forwarded to the primary provider. At 12 and 24 weeks, HbA1c is measured and the staff will assess outpatient follow-up, hospital readmission or emergency department visit, adherence to insulin and glucose monitoring, hyperglycemic and hypoglycemic events, and perform the DES-SF.

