**Secondary:**

- Difference in the change in HbA1c from baseline to 12 weeks (+/-2 weeks) post-discharge (%, mmol/l)
- Difference in the change in HbA1c from baseline to 12 and 24 weeks (+/-2 weeks) post-discharge (%, mmol/l)
- Difference in the change in fasting plasma glucose (FPG) from baseline to 12 and 24 weeks in DOS vs ESC (mg/dl)
- Difference in the % of patients achieving HbA1C 7% in DOS vs ESC (12, 24 weeks)
- Difference in the % of patients achieving HbA1C 6.5% in DOS vs ESC (12, 24 weeks)
- Difference in the % of patients achieving individualized HbA1C target in DOS vs ESC (12, 24 weeks)
- Difference in the proportion of patients with accurate and complete discharge orders for basal insulin and related supplies. (%)
  - Assessed as complete dose, quantity dispensed, adequate refills (separate for basal and prandial insulin), and correct prescription for pen needles (presence, quantity, adequate refills), no jargon
- Difference in the proportion of patients with accurate and complete discharge orders for prandial insulin and related supplies. (%)
  - Assessed as complete dose, clear dosing instructions, quantity dispensed, adequate refills, and correct prescription for pen needles (presence, quantity, adequate refills), no jargon
- Difference in the proportion of patients with a discharge prescription for glucose monitoring supplies (%)
- Difference in adherence to glargine U300 (% taking >80% of doses) at 2, and 24 weeks
- Difference in the proportion of patients who remain on glargine U300 at 24 weeks (%)
- Difference in the mean dose of glargine U300 at 2 and 24 weeks (units)
- Difference in the frequency of glucose monitoring at 2 and 24 weeks (times per day)
- Difference in the proportion of patients who follow up with their primary care provider or endocrinologist within 2, 6 weeks of discharge (%)
- Difference in the incidence of documented symptomatic (BG <54 mg/dl) hypoglycemia (%)

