## DEFINITIONS

**Serious adverse event (SAE)**: any untoward medical occurrence that at any dose:

- Results in death,
- Is life threatening, (Note: the term “life-threatening” refers to an event/reaction in which the patient was at risk of death at the time of the event/reaction; it does not refer to an event/ reaction which hypothetically might have caused death if it were more severe),
- Requires inpatient hospitalization or results in prolongation of existing hospitalization,
- Results in persistent or significant disability/incapacity,
- Is a congenital anomaly/birth defect, or
- Is a medically important event or reaction. Medical and scientific judgment should be exercised in deciding whether other situations should be considered serious, such as important medical events that might not be immediately life-threatening or result in death or hospitalization, but might jeopardize the patient or might require intervention to prevent one of the other outcomes listed in the definition above.

**Related Adverse Event**, i.e. **Adverse Drug Reaction (ADR)**: There is a reasonable possibility according to the investigator that the product may have caused the event.

**Unexpected Adverse Event**, i.e. **Adverse Drug Reaction (ADR)**: An adverse reaction, the nature or severity of which is not consistent with the applicable product information (package insert/summary of product characteristics for an approved product). An expected ADR with a fatal outcome should be considered unexpected.

**New safety finding**: Any safety issue that may require expedited reporting because providing information that may lead to a change in the known risk-benefit balance for the product and as mentioned, but not limited to, in the following regulatory texts: US: FDA: 21 CFR Parts 312 Investigational New Drug Application - Section 312.32, (c) (1) IND safety reports.

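### Severe hypoglycemia is worded inconsistently, and an assisted episode without seizure, hemodynamic compromise or a documented low reading enters neither hypoglycemia count

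*Combined protocol and SAP*

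**What the plan says.** Three places in the combined protocol and SAP bear on how a hypoglycemic episode is classified.

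- **Data and Safety Monitoring Plan (A.5), item 2.** Adverse events are to include "severe hypoglycemia rates (defined as hypoglycemia associated with seizure or hemodynamic compromise in need of outside assistance".
- **Appendix, discharge order set, Notify Physician.** A checkbox instruction tells the patient to call a provider for recurrent lows or "if you have any severe low sugars requiring the assistance of someone else to treat".
- **H.2.b Endpoints, Secondary.** The only hypoglycemia endpoint is "Difference in the incidence of documented symptomatic (BG <54 mg/dl) hypoglycemia", given as a percentage. The synopsis lists the same endpoint.

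The term also appears without a definition in two places. In the synopsis list of secondary endpoints, a history of severe hypoglycemia is one of the conditions that move a patient's HbA1c target from below 7% to below 8%. In the order set, it is one of the selection criteria for glucagon.

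On collection, Table 9 schedules a hypoglycemia review at 2, 6, 12 and 24 weeks. F.1.b and F.2.c have staff assess, at 12 and 24 weeks in each arm, "adherence to insulin and glucose monitoring, hyperglycemic and hypoglycemic events, and perform the DES-SF". On reporting, item 2 says "All adverse events and unanticipated problems will be reported to the IRB". The serious adverse event (SAE) definition includes an event that "Requires inpatient hospitalization or results in prolongation of existing hospitalization", and medically important events that "might jeopardize the patient or might require intervention to prevent one of the other outcomes listed in the definition above".

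**The concern.** The arms differ in how basal insulin is titrated. Section E, F.2.b and Table 7 give the discharge order set (DOS) arm a standard titration schedule, and leave titration to the discharge team in the enhanced standard care (ESC) arm. Hypoglycemia is therefore a natural harm to compare between them. The safety plan speaks of rates of severe hypoglycemia, so the event is meant to be counted, and the definition fixes what goes into the count.

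Need for another person's help is the feature the order set itself uses to mark a low as severe, yet no listed endpoint or adverse-event term counts assisted episodes as a category. In addition, Table 7 has a nurse make the follow-up calls in DOS and a coordinator make them in ESC, and no masking of the callers is described. Without a written rule for an assisted episode that has no glucose value, the two sets of callers may classify it differently.

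**Working it through.** The plan gives no figure on this point, so the check sets the definitions side by side.

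**Step 1: parse the safety-plan definition.** It can be read in two ways:

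- (a) seizure or hemodynamic compromise, and in either case outside assistance is needed;
- (b) seizure alone, or hemodynamic compromise that needs outside assistance.

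Both readings require seizure or hemodynamic compromise. Assistance alone qualifies under neither.

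**Step 2: parse the endpoint.** It requires symptoms and a documented glucose below 54 mg/dl. It sets no upper limit on severity and does not exclude assisted episodes.

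**Step 3: run assisted episodes through each definition.** Every row is an episode that another person had to treat.

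| Assisted episode | Severe-hypoglycemia term | Secondary endpoint | SAE |
|---|---|---|---|
| Seizure, or hemodynamic compromise; symptomatic reading <54 mg/dl documented | Yes | Yes | If a criterion is met |
| Seizure, or hemodynamic compromise; no such reading | Yes | No | If a criterion is met |
| Neither feature; symptomatic reading <54 mg/dl documented | No | Yes | If a criterion is met |
| Neither feature; no such reading; hospitalized or life-threatening | No | No | Yes |
| Neither feature; no such reading; treated at home | No | No | Only if judged medically important |

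The last row is the gap. An example is a patient too confused to self-treat whom a relative helps before anyone takes a reading. The order set's wording would call this severe. The safety-plan term and the endpoint would both leave it out. The row above it is also outside both hypoglycemia counts, but the SAE criteria capture it by definition.

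**Step 4: ask whether general reporting fills the last row.** Item 3 of the safety plan has all adverse events recorded and passed to the principal investigator, and item 2 has them sent to the IRB. The reporting section then says that expected, non-serious events go to the IRB only in summary at continuing review. A.2.b and the study risk assessment refer to adverse events related to the study. The medically important criterion rests on judgment. None of these sections sets up assisted hypoglycemia as a category or asks for a table of it by arm. The episode may well be written down, but no rule says how it is classified or counted.

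**Step 5: size.** An estimate would need the rate of assisted episodes, the share with neither seizure nor hemodynamic compromise, and the share of those without a documented low reading. The documents give none of the three.

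**The case against.** The strongest reply is that the plan casts a wider net than the severe-hypoglycemia term suggests. The adverse-event list in item 2 is not exclusive, hypoglycemia is reviewed at four time points with no severity threshold, and the 12- and 24-week wording is the same in both arms. The order-set line is an instruction on when to call, not an outcome definition. A call instruction can reasonably have a lower threshold than an adverse-event term, so the two lines do not contradict each other on any outcome. All of this stands. It makes the problem one of classification more than of collection, and it makes the order-set line evidence of loose terminology and no more than that. It does not supply a count of assisted episodes.

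Three stronger readings are tempting, and the documents do not support them.

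- *A reader might infer that serious episodes escape every definition.* They do not. Assisted episodes with a documented symptomatic value below 54 mg/dl are in the endpoint, and those that are hospitalized, life-threatening or judged medically important are SAEs.
- *A reader might infer that the narrow definition makes DOS look safer.* The definition applies to both arms. An equal undercount would make a difference harder to see, without specifically favoring DOS. If DOS caused more such episodes, leaving them out would shrink the visible absolute difference. On the other hand, nurse contact and the call instruction could raise ascertainment in DOS. The net direction is open.
- *A reader might assume a share of assisted episodes with seizure or hemodynamic compromise and call the remainder missed.* Such a share has no source in the documents, and the calculation would ignore capture through the endpoint and SAE reporting.

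**Conclusion.** The point holds in limited form. Severe hypoglycemia is worded in two ways and elsewhere left undefined. An assisted episode with no seizure, no hemodynamic compromise and no documented symptomatic glucose below 54 mg/dl is in neither of the plan's hypoglycemia counts, under either reading of the safety-plan definition. It reaches the safety data only through general adverse-event reporting or SAE judgment, with no count by arm.

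The number of such episodes cannot be estimated from the documents, and the direction of any bias is not established. The conclusion rests on the text alone and needs no assumed event rate. The primary HbA1c analysis is unaffected. The effect is on the completeness of the safety comparison and, through the undefined history term, on how clearly the individualized HbA1c target is assigned. It is worth correcting because the correction is cheap and the arms differ in titration.

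**What to change.** Reconcile the wordings for outcome purposes and state one definition of severe hypoglycemia, to be used also where a history of it sets the individualized HbA1c target. At each scheduled hypoglycemia review (2, 6, 12 and 24 weeks), in both arms and with the same questions, record whether another person's assistance was needed and whether a glucose value was available. Flag seizure or hemodynamic compromise as a subset of the assisted episodes. Tabulate assisted episodes and the flagged subset by arm, beside the existing endpoint.

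The cost is small: an assistance-needed field (with a note of whether a glucose value exists) on a review that already takes place, a short wording change, and slightly more events to record. Treatment and patient instructions do not change, and the call instruction in the order set can stay as it is.
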